8.3 Cost-effectiveness

The proposed cost–utility analysis will use decision modeling and sensitivity analysis techniques to ensure the robustness of the study's conclusions. Cost-effectiveness will be assessed using the incremental cost-effectiveness ratio, which is determined by calculating the difference in costs divided by the difference in QALYs between both treatment groups.

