1. INTRODUCTION AND RATIONALE

In the Netherlands, diagnostics and treatment of bone fractures and dislocations are generally organized in the secondary care setting. When a fracture or dislocation is presumed, most general practitioners refer the patient to an X-ray facility in a nearby hospital. When the fracture or dislocation is confirmed, an emergency care doctor or trauma surgeon generally provides the treatment and follow-up. In contrast, since January 2017 the general practice 'Zorgplein Lemmer' provides equal care for patients with non-complex fractures or dislocations. In this practice, regular X-ray diagnostics are used, which are digitally transmitted to the radiologist. When a non-complex fracture or dislocation (a so-called 'light trauma') is diagnosed, the for this purpose well-trained general practitioners provide the patient with the usual care (e.g. a splint or sling) and provides follow-up consults in his practice. While light trauma care is provided in several general practices in the Netherlands and healthcare professionals in both the general practice and the hospital are very satisfied with this provided care, it is unknown what the patient satisfaction level is and which determinants affect this patient satisfaction. Nowadays, substitution of care from the secondary to the primary care setting is stimulated by the government and insurers and in that light we aim to study the patient satisfaction of light trauma care for non-complex fractures or dislocations in the primary care setting in comparison to the secondary care setting. When the general practitioners in our study obtain similar results as the nearby hospitals, light trauma care may be substituted nationwide and beyond.

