3. STUDY DESIGN

This is an observational cohort study including patients presenting at the X-ray facility in the general practice Zorgplein Lemmer and patients presenting at the X-ray facility of the Antonius Hospital Sneek, with an X-ray confirmed diagnosis of a non-complex fracture or dislocation and planned to be treated in either the Zorgplein Lemmer or Antonius Hospital Sneek. Patients aged 11 years or younger, and/or presenting outside ordinary business hours are excluded, due to possible inclusion bias. After inclusion the follow-up questionnaires continue for 12 weeks. The total duration of the study is 18 months.

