5. TREATMENT OF SUBJECTS

5.1 Investigational product/treatment

Treatment in the general practice is identical to treatment in the hospital and is equal to the national guidelines. Those are described in the online treatment protocol 'Behandelprotocollen Lichte traumazorg in de eerste lijn'. This study has no impact on speed, choice, location or execution of diagnostics or treatment and thus is an observational study.

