6.1.2 Secondary study parameters/endpoints

1. Patient satisfaction measured using the PSQ-18 (1 and 6 weeks after treatment).

Marshall GN Hays RD. The Patient Satisfaction Questionnaire Short-Form (PSQ-18). Santa Monica, CA: RAND, 1994.

2. Complications of treatment and pain scores (12 weeks after treatment).
3. Physical functioning according to the 12-item World Health Organisation (WHO) Disability Assessment Schedule II (12 weeks after treatment).

*World Health Organization Disability Assessment Schedule II (WHO-DAS II)
WHO, Geneva (2000) www.who.int/icidh/whodas/whodasversions/12int.pdf*

4. Limitations in functions of upper extremities (if applicable) according to the Disabilities of the Arm, Shoulder and Hand (DASH) questionnaire (12 weeks after treatment).

5. General health status according to the 12-item General Health Questionnaire (GHQ-12; 12 weeks after treatment).

Goldberg, D. P. (1972). The Detection of Psychiatric Illness by Questionnaire. Maudsley Monograph No. 21. Oxford University Press: Oxford.

6. Quality of life using the EQ5D questionnaire (12 weeks after treatment).

Euroqol Group (1990) Euroqol—a new facility for the measurement of health-related quality of life. Health Policy 16:199–208

7. Time consumption (waiting time, treatment time, travelling time and distance; 1, 6, and 12 weeks after treatment).

8. Costs (12 weeks after treatment).

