8.2 Secondary analyses

Secondary analyses will be conducted using data from all enrolled patients. Initially, univariable statistical tests (eg, χ^2 test or Fisher's exact test for categorical variables; t test or Wilcoxon rank-sum test for continuous variables) will be used to evaluate differences in outcome scores between the two treatment groups. Subsequently, data will be analyzed using multivariable regression models to estimate differences in mean patient satisfaction scores using possible predictors (eg, complications, pain scores, physical functioning, EQ-5D, time consumption) between both treatment groups.

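### Section 8.3 judges cost-effectiveness only by a cost-per-QALY ratio, although the plan's own premises make a near-zero QALY difference likely

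*Combined protocol and SAP*

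**What the plan says.** Section 8.3 names one criterion: "Cost-effectiveness will be assessed using the incremental cost-effectiveness ratio", determined by "calculating the difference in costs divided by the difference in QALYs between both treatment groups". On uncertainty it says only that the analysis "will use decision modeling and sensitivity analysis techniques to ensure the robustness of the study's conclusions". It names no specific technique, model horizon, interval method or willingness-to-pay threshold. It gives no rule for a QALY difference that is close to zero or negative.

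Elsewhere the plan gives reasons to expect little difference in health outcome. Section 5.1 states: "Treatment in the general practice is identical to treatment in the hospital and is equal to the national guidelines". Section 6.3 adds that care in the general practice follows the hospital's own standard. The Introduction sets out the result that would matter for policy: "When the general practitioners in our study obtain similar results as the nearby hospitals, light trauma care may be substituted nationwide and beyond". Section 3 limits observation: "After inclusion the follow-up questionnaires continue for 12 weeks". Section 4.4 sizes the study on patient satisfaction, with 100 patients per group; costs and QALYs play no part in that calculation.

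**The concern.** A ratio is a poor decision statistic when its denominator may be zero. Small chance movements in the QALY difference then produce very large swings in the ICER, including changes of sign. A confidence interval for the ratio by Fieller's method is unbounded whenever the QALY difference is not significantly different from zero.

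The sign does not identify the conclusion either. A negative ICER can mean that general practice care is cheaper and better, or that it is dearer and worse. A positive one can mean dearer and better, or cheaper and worse.

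Similar outcomes at a different cost is the result that the plan would use to argue for substitution. It is also the result for which the only named cost-effectiveness statistic behaves worst. Without a prespecified alternative, the summary could be chosen after seeing where the estimate falls.

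**Working it through.** **1. The plan's own figure.** The documents give no figure for costs, QALYs or the ICER. The one calculable figure is the sample size. For an effect size of 0.4, two-sided alpha 0.05 and 80% power, n per group = 2 × (1.96 + 0.84)² / 0.4² ≈ 98, or 99 using unrounded quantiles and rounding up. The total is 198 against the stated 200. With 100 per group, power is 80.7% (normal) or 80.4% (t test). The figure reproduces, and 100 per group is used below.

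**2. Inputs.** From the documents: 100 per group (4.4) and 12 weeks of follow-up (3), which is 12/52 = 0.231 year. Assumed, because the documents are silent:
- utility SD 0.10 to 0.25, with a utility difference constant over the 12 weeks;
- mean saving EUR 200 per patient and cost SD EUR 500;
- normal, independent estimates of the two differences;
- no confounding.

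**3. Standard error of the QALY difference.** SE = SD × (12/52) × √(2/100). For SD 0.10 this is 0.10 × 0.231 × 0.1414 = 0.0033. For SD 0.25 it is 0.0082.

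**4. Probability that the denominator has the wrong sign.** P = Φ(−true difference / SE). The factor 12/52 appears in both terms and cancels. When the true difference is zero there is no right sign: the estimate falls on each side with probability 0.50, whatever the SD.

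| Utility SD | SE (QALY) | True utility difference 0 (either side) | 0.01 (0.0023 QALY) | 0.02 (0.0046 QALY) |
|---|---|---|---|---|
| 0.10 | 0.0033 | 0.50 | 0.24 | 0.08 |
| 0.15 | 0.0049 | 0.50 | 0.32 | 0.17 |
| 0.20 | 0.0065 | 0.50 | 0.36 | 0.24 |
| 0.25 | 0.0082 | 0.50 | 0.39 | 0.29 |

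For the wrong-sign probability to fall below 2.5%, the true utility difference must exceed 1.96 × SD × √(2/100). That is 0.028 for SD 0.10 and 0.069 for SD 0.25.

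**5. Spread of the ratio.** In 400,000 simulated studies with utility SD 0.20 and true QALY difference 0, the central 95% of ICERs ran from about −497,000 to +487,000 EUR per QALY. It was wider for SD 0.10 (about −960,000 to +982,000) and narrower for SD 0.25 (about −389,000 to +392,000).

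**6. Net benefit on the same inputs.** Incremental net monetary benefit = λ × QALY difference − cost difference, where λ is the threshold. Its SE is √[(λ × SE of QALY difference)² + (SE of cost difference)²]. The SE of the cost difference is 500 × √(2/100) = 70.7. At an assumed λ of EUR 20,000 the mean is 200, with SE √(65.3² + 70.7²) = 96 for SD 0.10 and √(130.5² + 70.7²) = 149 for SD 0.20. Both are finite, and the sign has one meaning.

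**7. A second set of assumptions.** Take a 12-week QALY SD of 0.03, cost SD EUR 400 and saving EUR 100. The SE of the QALY difference is 0.03 × √(2/100) = 0.0042. At a true gain of 0.002 the wrong-sign probability is Φ(−0.47) = 32%. At λ = EUR 20,000 the net-benefit SE is √(84.9² + 56.6²) = 102. The pattern is the same.

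**The case against.** **The near-zero difference is an inference.** This stands. The plan gives no expected QALY difference, and its sentence about similar results is conditional. Section 6.3 describes different providers and follow-up arrangements. Patients are not randomised and are grouped by where they are recruited, so case mix could move the observed difference away from zero. A difference produced by confounding would not make the ICER more meaningful, however.

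**Decision modelling may cover this.** Probabilistic sensitivity analysis would yield a joint cost–QALY distribution, from which net benefit and an acceptability curve follow. Section 8.3 does not exclude it. It does not commit to it either, and the criterion it names remains the ratio. A horizon longer than 12 weeks would change the scale of the QALY difference, but not the expectation of none if treatment is identical.

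**Net benefit may be no more conclusive.** This also stands. Under the second set of assumptions, net benefit is 100 with SE 102, a 95% CI of about −100 to +300. The cost difference alone is 100 with SE 56.6, so z is about 1.8 against 1.0. The gain is in interpretability, not precision, and so the separate differences must be reported too.

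**Two stronger readings are not supported.** A reader might infer that the plan has no way to show equal QALYs with different costs. It does have one: costs and EQ-5D are separate endpoints in 6.1.2, and 8.2 compares outcomes between groups. A reader might also infer that costs will be tested by rank sums, since 8.2 offers a "t test or Wilcoxon rank-sum test for continuous variables". That list is given as examples for outcome scores generally, puts the t test first, and does not assign the Wilcoxon test to costs.

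**Conclusion.** The point holds in a limited form. Section 8.3 relies on the ICER alone and has no provision for a QALY difference near zero, which is a foreseeable result if the plan's premises are right. At a true difference of zero, the 50% chance of falling on either side does not depend on any assumed SD. The other figures do rest on assumptions: 24% to 39% wrong sign at a true utility difference of 0.01, and an ICER spread of hundreds of thousands of euros per QALY in both directions. They are illustrations of size, not predictions. The effect is confined to a secondary analysis; the satisfaction endpoint and its sample size are untouched. It should nevertheless be settled before analysis, because substitution of care is the study's stated motive.

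**What to change.** In 8.3:
- Make incremental net monetary benefit the decision statistic, with 95% CIs over a stated range of willingness-to-pay thresholds.
- Report the mean cost difference and the mean QALY difference separately, each with a bootstrap CI.
- Add a cost-effectiveness plane and an acceptability curve.
- Report the ICER only when the QALY difference is clearly away from zero, under a rule fixed in advance (for example, that its 95% CI excludes zero).
- Name the sensitivity-analysis technique and the model horizon.

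The cost is some SAP wording and a few hours of programming, with no data beyond what the ICER already needs. The downside is that a threshold range has to be stated and justified. Net benefit will not correct case-mix differences between the settings. Nor does it solve the problem that EQ-5D is collected only once, at 12 weeks, so QALYs need further assumptions under either statistic. Both need their own provision.

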9. ETHICAL CONSIDERATIONS

9.1 Regulation statement

The study will be executed according to law (WMO). All data will be processed and saved anonymously.

9.2 Recruitment and consent

Patients have sufficient time (approximately several hours between the moment of referral by the general practitioner, the moment when the assessment of eligibility is performed by participating general practitioners near Lemmer, who will approach each potential study patient and inquire about their interest and eligibility in participating in this study and the moment of X-ray diagnostics and composing a treatment plan) to ask questions and to consider participation. Patient information, website and informed consent forms are easy-to-read. Patients are allowed to withdrawal at any moment without consequences for their treatment plan or follow-up consultations.

9.3 Benefits and risks assessment, group relatedness

This is an observational cohort study consisting of questionnaires, thus there are hardly any risks associated with participation in this study. The burden of patients is considered as low because the study only consists of questionnaires (in total about 1.5 hours).

9.4 Compensation for injury

Because all interventions in this study (the questionnaires) are non-invasive, there is no obligatory insurance for a liability insurance.

9.5 Incentives

Participants have no (extra) costs by participating in this study. There is no compensation for participation in this study.

10. ADMINISTRATIVE ASPECTS AND PUBLICATION

10.1 Handling and storage of data and documents

All data is processed anonymously. All participants are coded and blinded.

10.2 Annual progress report

At their request, the METC may receive an annual report stating inclusion of participants, questionnaires completed, and adverse events.

10.3 End of study report

Researchers will inform the METC about the end of the study within 8 weeks after the last inclusion. The end of the study is defined as the last inclusion. When the study is terminated beforehand, the researchers will inform the METC.

Within a year after the end of the study the researchers will report the results of the study to the METC.

10.4 Public disclosure and publication policy

Publication(s) about this study will never contain personal data of individual participants.
